6.3.2 Disease Parameters

- Measurable is defined as any of the following: serum M-protein is ≥ 1 g/dL or "measurable" urine M-spike is ≥ 200 mg/24 hours or serum kappa or lambda FREE light chain of 10 mg/dL along with an abnormal kappa to lambda free light chain ratio.
- The serum free light chain (FLC) assay is of particular use in monitoring response to therapy in patients who have oligo-secretory disease. When using this assay, it is important to note that the FLC levels vary considerably with changes in renal function and do not solely represent monoclonal elevations. Thus both the level of the involved and the uninvolved FLC isotype (i.e., the involved/uninvolved ratio or involved-uninvolved difference) should be considered in assessing response. The serum FLC assay should be used in assessing response only if the baseline serum and/or urine M proteins are not "measurable" by traditional criteria (serum M protein ≥ 1 gm/dL and/or urine M

protein ≥ 200 mg/24), and the baseline level of the involved FLC is ≥ 10 mg/dL and clonal (abnormal ratio). Patients included on the study on the basis of FLC alone (i.e., no measurable serum/urine) should be the only ones who are evaluated using FLC response criteria. The others should follow usual criteria and ignore FLC results.

- In order to be classified as a hematologic response, confirmation of serum monoclonal protein, serum immunoglobulin free light chain (when primary determinant of response) and urine monoclonal protein (when primary determinant of response) results must be made by verification on two consecutive determinations.
- Caution must be exercised to avoid rating progression or relapse on the basis of variation of radiological technique alone. Compression fracture does not exclude continued response and may not indicate progression. When progression is based on skeletal disease alone, it should be discussed with the PI before removing the patient from the study.
- Appearance of monoclonal or oligoclonal bands that are different from original isotype may not be defined as “relapse from CR”. Oftentimes, such bands may indicate fluctuations in immunological parameters that are not reflective of MM disease. In these situations, immunofixation and electrophoresis will be interpreted by the clinician before being labeled as “relapse”[\(30\)](#).

6.3.3 Response Criteria from International Myeloma Working Group Criteria[\(31\)](#) and addition of nCR category[\(6, 21\)](#):

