6.3.3.1 Evaluation of Response Criteria

- **Stringent Complete Response (sCR)**

Complete Response as defined below plus:

Normal FLC ratio and absence of clonal cells in bone marrow by immunohistochemistry or immunofluorescence (presence/ absence of clonal cells is based on the kappa/ lambda ratio.

- **Complete Response (CR)**

Negative immunofixation on the serum and urine and disappearance of any soft tissue plasmacytomas and $\leq 5\%$ plasma cells in bone marrow

- **Near Complete Response (nCR)**

Defined as absence of myeloma protein on electrophoresis, independent of immunofixation status[\(6, 21\)](#)

- **Very Good Partial Response (VGPR)**

Serum and urine M-protein detectable by immunofixation but not on electrophoresis or 90% or greater reduction in serum M-protein plus urine M-protein level < 100 mg per 24h. If the serum and urine M-protein are unmeasurable, a $\geq 90\%$ decrease in the difference between involved and uninvolved FLC levels is required in place of the M-protein criteria.

- **Partial Response (PR)**

$\geq 50\%$ reduction of serum M-protein and reduction in 24-h urinary M-protein by $\geq 90\%$ or to < 200 mg per 24h. If the serum and urine M-protein are unmeasurable, a $\geq 50\%$ decrease in the difference between involved and uninvolved FLC levels is required in place of the M-protein criteria

- **Stable Disease (SD)**

Not meeting criteria for CR, VGPR, PR or progressive disease. All categories also require no known evidence of progressive or new bone lesions if radiographic studies

were performed. Radiographic studies are not required to satisfy these response requirements.

- **Progressive disease (PD)**

Requires any one or more of the following:

Increase of $\geq 25\%$ from lowest response value in the following on 2 consecutive measurements:

- Serum M-component and/or (the absolute increase must be ≥ 0.5 g/dl). The serum M-component increases of ≥ 1 gm/dl are sufficient to define relapse if starting M-component is ≥ 5 g/dl.
- Urine M-component and/or (the absolute increase must be ≥ 200 mg/24h
- Only in patients without measurable serum and urine M-protein levels: the difference between involved and uninvolved FLC levels. The absolute increase must be >10 mg/dl.
- Bone marrow plasma cell percentage: the absolute % must be $\geq 10\%$
- Definite development of new bone lesions or soft tissue plasmacytomas or definite increase in size of existing bone lesions or soft tissue plasmacytomas

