6.3.7 Overall response rates after 8 cycles

Overall response rates (ORR) is PR+VGPR+CR after 8 cycles of therapy.

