10.3 STATISTICAL ANALYSES

10.3.1 Analysis of the Primary Endpoints

The 90% and 95% confidence intervals will be constructed around the observed fraction of patients with grade 3+ neurologic toxicity, and will be reported along with the observed incidence. If 5/45 are noted to have grade 3+ neurologic toxicity, the exact two-sided 90% CI bound extends from 4.5% to 22.0%, thus confirming that this rate of toxicity is likely to exceed 5%, and is consistent with as high as 22%.

As an early stopping rule for toxicity for the first 20 patients: if 4 patients are found to have grade 3+ neurologic toxicity in the first two completed cycles of treatment, no further patients will be enrolled. As soon as this can be determined, since the lower 80% one-sided confidence bound around 4/20 is 11.7%, which, being greater than 10%, would be considered demonstration of excessive toxicity. In fact, the lower 80% bounds range from 67% for observing 4 patients with grade 3+ neurologic toxicity in the first 4 patients to 12% for observing 4 patients with grade 3+ neurologic toxicity in 20 patients.

The rates of VGPR+CR and CR alone will also be estimated and reported. These rates are expected to be fairly high. Two-sided 95% confidence interval bounds will be formed around each of these measures.

In order to allow for a small number of inevaluable patients, the accrual ceiling will be set at 50.

It is anticipated that 2-3 patients per month may enroll on this trial; thus, 2 years is anticipated as the accrual period for this study.

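### nCR overlaps VGPR and CR but is left out of the VGPR+CR and ORR sums, so a literal count can drop good responders

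*Combined protocol and SAP*

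**What the plan says.** The heading of 6.3.3 announces the IMWG criteria and the "addition of nCR category". Section 6.3.3.1 then lists the categories in the order sCR, CR, nCR, VGPR, PR, SD. The definitions that matter here are:

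- **CR:** "Negative immunofixation on the serum and urine and disappearance of any soft tissue plasmacytomas", with at most 5% plasma cells in the marrow. sCR is CR plus further conditions.
- **nCR:** "Defined as absence of myeloma protein on electrophoresis, independent of immunofixation status". It carries no marrow or plasmacytoma condition.
- **VGPR, first route:** "Serum and urine M-protein detectable by immunofixation but not on electrophoresis".
- **VGPR, second route:** "90% or greater reduction in serum M-protein plus urine M-protein level" below 100 mg per 24 h. A free light chain (FLC) criterion replaces this when serum and urine M-protein are unmeasurable.

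The planned summaries name fewer categories. Section 10.3.1 says: "The rates of VGPR+CR and CR alone will also be estimated and reported", and "Two-sided 95% confidence interval bounds will be formed around each of these measures". Section 6.3.7 says: "Overall response rates (ORR) is PR+VGPR+CR after 8 cycles of therapy". The SD definition rules out CR, VGPR, PR and progression. None of these names nCR. Nothing in the protocol says that the categories are exclusive, which label prevails when two apply, or where nCR is counted.

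**The concern.** Two categories describe the same laboratory result, and only one of them enters the sums. An electrophoresis-negative, immunofixation-positive patient is VGPR by one line of 6.3.3.1 and nCR by another. Since nCR is listed above VGPR and the objective in 1.1.2 is best response, the natural assignment is nCR. Read as written, that patient then counts in neither VGPR+CR nor ORR, while a patient with a 90% fall and a visible band counts in both. The better responder would lower the rate.

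The trial has already used nCR as a class of its own. The interim summary in 1.2.10 lists nCR/sCR apart from VGPR and still counts those patients in ORR. At stake are the response rates that will be quoted, with their intervals, and set beside other regimens.

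**Working it through.** **Inputs.** Definitions: 6.3.3.1. Sums: 10.3.1 and 6.3.7. Interim counts for the first 20 patients: 1.2.10. Results of the earlier study of the combination in newly diagnosed patients: 1.2.6. Evaluable patients, 45: 10.2.

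**1. Reproduce the interim figures.** nCR/sCR 15/20 = 75%; VGPR 2/20 = 10%; PR 2/20 = 10%; SD 1/20 = 5%; the counts sum to 20. ORR = (15 + 2 + 2)/20 = 19/20 = 95%, as stated. This figure requires nCR to count as a response, although 6.3.7 does not list it.

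**2. Apply the definitions to each electrophoresis-negative result.**

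| Immunofixation | Marrow and plasmacytoma conditions | nCR | CR | VGPR, first route |
|---|---|---|---|---|
| positive | any | yes | no | yes |
| negative | met | yes | yes | no |
| negative | marrow above 5% or not done | yes | no | no |

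Every first-route VGPR is also nCR. The patient in the last row reaches VGPR only through the reduction route.

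**3. Count under three rules.** Let k be the number of nCR-only patients among the interim 15. The protocol does not give k; it can be 0 to 15.

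- A. nCR counted within VGPR or better, not as CR: VGPR+CR = (15 + 2)/20 = 17/20 for any k; CR = (15-k)/20; ORR = 19/20.
- B. Highest listed category, sums read literally: VGPR+CR = (17-k)/20; CR = (15-k)/20; ORR = (19-k)/20.
- C. nCR pooled with CR: VGPR+CR = 17/20; CR = 15/20; ORR = 19/20.

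**4. Put in an assumed k = 5.** The intervals are exact two-sided 95% (Clopper-Pearson): lower limit = the 0.025 quantile of Beta(x, n-x+1), upper limit = the 0.975 quantile of Beta(x+1, n-x).

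| Rule | VGPR+CR | CR alone | ORR |
|---|---|---|---|
| A | 17/20 = 85% (62.1-96.8) | 10/20 = 50% (27.2-72.8) | 95% |
| B | 12/20 = 60% (36.1-80.9) | 10/20 = 50% (27.2-72.8) | 14/20 = 70% |
| C | 17/20 = 85% (62.1-96.8) | 15/20 = 75% (50.9-91.3) | 95% |

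Each relabelled patient moves a rate by 1/20 = 5 points at the interim and by 1/45 = 2.2 points at full size.

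**5. Is k = 5 a sensible illustration?** In the earlier study 62% reached at least nCR and 42% sCR. The nCR-only share of the top group was thus at most (62-42)/62 = 32%, because the gap also holds any CR that was not sCR. Applied to 15 patients, 0.32 x 15 = 4.8. That study reports a median of 12 cycles and the interim a median of 7, so the share need not carry over. k = 5 remains an assumption.

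**The case against.** The strongest reply is that the protocol can be read in a way that works. nCR is an addition to the IMWG list, 1.1.2 and 10.3.2 tie response to IMWG criteria, and the ORR sum, the SD definition and 10.3.1 use IMWG tiers only. On that reading one counts whoever meets the VGPR or CR criteria and ignores the nCR label. The interim VGPR+CR is then 17/20 whatever k is, apart from any patient in the last row of the first table who does not meet the reduction route. This is a fair reading, and probably what was meant. But it is written nowhere, and 1.2.10 lists VGPR separately from nCR, which points to assignment by highest category.

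A second reply concerns CR alone, and it stands. A patient positive on immunofixation cannot be CR, and a patient who meets CR keeps that status although nCR is also met. A reader might infer that both rates in 10.3.1 are undetermined. The documents do not support that: CR alone changes only if someone counts nCR as CR. No section permits this, although the pooled interim line could invite it.

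A reader might also take from the interim counts that VGPR+CR could lie anywhere from 2/20 to 17/20, and CR alone from 0/20 to 15/20, through labelling alone. That is not supported either. The low ends need k = 15, that is, no sCR or CR at all in a group reported as nCR/sCR. Most of that range is the unreported split; for a given k, labelling moves each rate by k/20.

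**Conclusion.** The point holds for VGPR+CR and for ORR. The definitions overlap by their own wording, the sums omit nCR, and assigning the best category, which is the natural rule, makes the literal sums wrong. (sCR is also unnamed in the sums, but harmlessly, since it is nested in CR.) For CR alone the risk is confined to pooling.

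The size depends on k, which the protocol does not report. With the assumed k = 5, labelling moves the interim VGPR+CR by 25 points, and pooling moves CR alone by the same amount. With k = 0 nothing moves. These rates are descriptive: they have intervals but no threshold or decision rule. The neurologic toxicity endpoint, the sample size of 45 and the stopping rule do not use response categories and are unaffected. The wording should be settled before the final response rates are reported.

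**What to change.** - **6.3.3.1:** state the hierarchy sCR > CR > nCR > VGPR > PR, each patient counted once in the highest category met. Define nCR as electrophoresis-negative and not meeting CR. Keep the existing VGPR criteria, including the FLC route, for patients not classed as nCR or better. Patients followed by FLC alone under 6.3.2 should stay on the FLC criteria, so that a blank electrophoresis does not by itself make them nCR.
- **10.3.1:** define the two rates as VGPR or better (VGPR+nCR+CR+sCR) and CR or better (CR+sCR).
- **6.3.7:** define ORR as PR or better, including nCR and sCR.
- **Reporting:** show nCR and sCR on separate lines.
- **Missing tests:** do not count a patient as CR when immunofixation or marrow is missing. This matters because 3.3.7.3 limits later serum immunofixation to patients in whom it is clinically indicated. Footnote o of the study calendar (3.4) already lets an earlier MRD-negative marrow stand during extended dosing; the new rule should refer to it.

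A simpler split, with nCR requiring positive immunofixation and VGPR requiring a visible band, would not do. A patient negative on both tests whose marrow is above 5% or was not taken would fit none of CR, nCR or VGPR.

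The cost is wording in three sections and splitting the interim nCR/sCR figure from patient records. Where immunofixation was not done, some patients will stay at nCR because CR cannot be shown.

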- Development of hypercalcemia that can be attributed solely to the plasma cell proliferative disorder

- **Relapse from CR**

Any one or more of the following:

- Reappearance of serum or urine M-protein by immunofixation or electrophoresis. (Appearance of monoclonal or oligoclonal bands that are different from original isotype may not be defined as “relapse from CR”. Oftentimes, such bands may indicate fluctuations in immunological parameters that are not reflective of MM disease. In these situations, immunofixation and electrophoresis will be interpreted by the clinician before being labeled as “relapse”. ([32](#), [33](#)))
- Development of $\geq 5\%$ plasma cells in the bone marrow
- Appearance of any other sign of progression (i.e., new plasmacytoma, lytic bone lesion, hypercalcemia)

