6.3.4 Duration of Best Response

The duration of overall response is measured from the time measurement criteria are met for best response until the first date that recurrent or progressive disease is objectively documented.

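### Relapse from CR can be scored on one unconfirmed original-isotype band, whereas laboratory response and laboratory or marrow progression need two consecutive results; this can only shorten duration of response in CR patients

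*Combined protocol and SAP*

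**What the plan says.** All the rules are in section 6.3 of the combined protocol and SAP.

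- **Response (6.3.2).** For a hematologic response, the M-protein or free light chain "results must be made by verification on two consecutive determinations".
- **Progression (6.3.3.1).** Rises in serum or urine M-component, free light chain difference or marrow plasma cells must be at least 25% "from lowest response value in the following on 2 consecutive measurements", with absolute minimums such as 0.5 g/dl in serum. New or larger bone lesions or plasmacytomas, and hypercalcemia, need no repeat.
- **Relapse from CR (6.3.3.1).** The requirement is "Any one or more of the following", and the first item is "Reappearance of serum or urine M-protein by immunofixation or electrophoresis". No repeat and no minimum is stated. The same bullet adds a carve-out: "Appearance of monoclonal or oligoclonal bands that are different from original isotype may not be defined as" relapse from CR, and in those situations "immunofixation and electrophoresis will be interpreted by the clinician before being labeled as" relapse.
- **Duration of response (6.3.4).** It runs from best response "until the first date that recurrent or progressive disease is objectively documented". Section 10.3.2 estimates it by Kaplan-Meier.
- **PFS (6.3.5).** The events are progression and death. Relapse from CR is not named.

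**The concern.** CR requires negative immunofixation, and relapse from CR is triggered by positive immunofixation. Entry and exit therefore share one cut-off on a yes/no assay, with nothing to absorb a faint band that appears once and is gone at the next test. The plan confirms the neighbouring laboratory calls but not this one.

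The consequence runs against depth of response. Under 6.3.3.1, M-protein seen on immunofixation but not on electrophoresis fits VGPR, and nCR disregards immunofixation altogether. A CR patient with a one-off trace band of the original isotype is scored as relapsed on a day when the same result fits VGPR or nCR. A patient already in VGPR or nCR with that result has no event. Duration of response would then pool responders judged by different failure standards, with the easiest failure standard applied to the deepest responders. A single-positive rule can add an event or bring one forward but can never remove one, so the effect has one direction.

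**Working it through.** The plan states no figure on this point, so there is none to reproduce. The check is a comparison of texts, followed by an illustration of size.

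**1. The rules side by side**

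| Call | Repeat required? | Minimum amount? |
|---|---|---|
| Laboratory response (6.3.2) | Yes, two consecutive | Set by response category |
| Laboratory or marrow progression (6.3.3.1) | Yes, two consecutive | Yes |
| Bone lesion, plasmacytoma or hypercalcemia progression (6.3.3.1) | No | Not applicable |
| Relapse from CR, different-isotype band (6.3.3.1) | Exempt; clinician interprets | Not applicable |
| Relapse from CR, original-isotype band (6.3.3.1) | None stated | None stated |

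The last row is the gap.

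**2. Assessments at risk**

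Take a patient who meets CR at Cycle 6 and has it confirmed at Cycle 7. A positive result at Cycle 7 would mean that CR was never confirmed, so Cycle 7 is not at risk. The later assessments in 6.3.1 are Cycles 8, 9, 12, 15, 18, 21, 24, 27, 30 and end of 32, which makes 10.

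**3. Which tests are done at those visits**

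- Serum: 3.3.7.3 restricts serum immunofixation after baseline to patients in whom it is clinically indicated.
- Urine: 3.3.7.4 and note m of the study calendar keep urine immunofixation on day 1 of Cycles 1-8 and of every third cycle in extension. Note m adds treatment termination.

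The trigger is serum or urine, so routine exposure is mainly through urine. Ten is the most for one test stream.

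**4. Chance of a false relapse**

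Let f be the chance, per assessment, of a transient original-isotype band in a patient otherwise in continuous CR. The documents do not give f. It is assumed here at 0.5% to 5%, independent between assessments.

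- Single positive: 1 - (1 - f)^10.
- Two consecutive positives: 1 - S(10), where S(n) = (1 - f) S(n-1) + f(1 - f) S(n-2) and S(0) = S(1) = 1. As a rough check, there are 9 adjacent pairs, so the result must be a little below 9f². At f = 1% that bound is 9 × 0.0001 = 0.09%.

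| f (assumed) | Single positive | Two consecutive |
|---|---|---|
| 0.5% | 1 - 0.995^10 = 4.9% | 0.02% |
| 1% | 1 - 0.99^10 = 9.6% | 0.09% |
| 2% | 1 - 0.98^10 = 18.3% | 0.35% |
| 5% | 1 - 0.95^10 = 40.1% | 2.1% |

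Fewer immunofixations lower both columns. If a faint band tends to persist from one visit to the next, the right-hand column rises and confirmation helps less.

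**The case against.** The strongest reply is that the text is silent rather than permissive. It does not say that one test suffices. Section 6.3.4 asks that recurrence be objectively documented, and recurrent is never defined as relapse from CR. The criteria are attributed to a published consensus that may settle the matter but cannot be checked from these documents. This stands as a caution on wording. It does not close the gap: confirmation is written out for the neighbouring laboratory criteria and absent here, relapse from CR is the natural reading of recurrent, and two analysts could derive different dates from one record.

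Second, testing is sparser than a visit count suggests, because repeat serum immunofixation is not routine. That stands and lowers the exposure, but scheduled urine immunofixation remains.

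Third, f is assumed, and a tenfold range of f gives a wide range of results. That also stands. The figures show how the rule behaves, not what happened in this trial.

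Stronger readings that a reader might infer are not supported:

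- *Any faint band ends response.* Different-isotype bands are exempt.
- *Progression always needs two results.* It does not for "Definite development of new bone lesions or soft tissue plasmacytomas or definite increase in size of existing bone lesions or soft tissue plasmacytomas", nor for hypercalcemia.
- *The patient is still in CR on the day of the band.* CR requires negative immunofixation, so the patient is in CR again only if the next test is negative.
- *Most responders are exposed.* The interim summary in 1.2.10 pools nCR with sCR, so the number in CR is not known.

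**Conclusion.** The inconsistency is real and worth correcting. Read as written, one transient original-isotype band on immunofixation ends duration of response for a patient in CR, without the confirmation that the plan requires for laboratory response and for laboratory or marrow progression.

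Its scope is narrow. Duration of response is a secondary endpoint. The primary toxicity endpoint, the sample size and overall survival are unaffected. A reader might infer that PFS is biased as well. The documents support that only if relapse from CR is counted as progression, which 6.3.5 does not say.

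The direction is certain under the literal reading; the size is not. The table of false-relapse chances depends on the assumed f, on independence between assessments, and on immunofixation being done at all 10 visits. It does not establish that the trial's estimate is materially wrong.

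**What to change.** For endpoint scoring only:

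1. In 6.3.3.1, Relapse from CR, limit the first item to M-protein of the original isotype and, after "Reappearance of serum or urine M-protein by immunofixation or electrophoresis", add: *on 2 consecutive measurements; the relapse date is the date of the first of the two*. Leave plasmacytoma, lytic lesion and hypercalcemia as they are.
2. In 6.3.4, state that recurrent means relapse from CR as so defined.
3. In 6.3.5, state whether relapse from CR counts as progression for PFS.
4. Report duration of response on this definition, with the single-positive version as a sensitivity analysis.

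The cost is a few sentences and a re-derivation of relapse dates from results already collected. Dating from the first positive avoids delaying confirmed relapses. The downside is that a positive at the last assessment stays unconfirmed and is censored unless the test is repeated. The same holds for a serum positive with no later immunofixation, since serum repeats are not routine. The number of unconfirmed positives should be reported.

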6.3.5 Progression-Free Survival

PFS is defined as time of start of treatment to time of progression or death, whichever occurs first.

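### The CR and relapse-from-CR definitions both include 5% marrow plasma cells, so a patient already in CR whose later marrow reads exactly 5% meets both

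*Combined protocol and SAP*

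**What the plan says.** Section 6.3.3.1 (Evaluation of Response Criteria) defines CR as "Negative immunofixation on the serum and urine and disappearance of any soft tissue plasmacytomas and $\leq 5\%$ plasma cells in bone marrow". Stringent CR is built on it: "Complete Response as defined below plus" a normal free light chain ratio and no clonal cells in the marrow.

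The same section introduces relapse from CR with "Any one or more of the following". One item on that list is "Development of $\geq 5\%$ plasma cells in the bone marrow".

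Section 6.3.4 measures duration of response from the time the best-response criteria are met "until the first date that recurrent or progressive disease is objectively documented". Section 10.3.2 makes this a secondary endpoint, estimated by Kaplan-Meier with 95% confidence intervals. Section 6.3.5 defines PFS as "time of start of treatment to time of progression or death, whichever occurs first".

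**The concern.** A response state and the event that ends it should not share a value. Here they share 5%, and the marrow criterion needs no other sign of disease to count as relapse. For a patient already in CR, one marrow report can support two opposite entries: response continuing, or response ended on that date.

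What is at stake is the duration-of-response curve. Two analysts following the same text could give the same patient either an event at the date of the 5% reading or continued follow-up to a later event or censoring. If the choice is left to case-by-case judgement, it may be made with the patient's later course already known.

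**Working it through.** No figure in the plan depends on this point, so there is nothing to recompute. The check sets the definitions side by side.

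**Inputs, all from Section 6.3.3.1**
- CR, marrow component: ≤ 5%, that is [0, 5].
- Relapse from CR, marrow component: ≥ 5%, that is [5, 100].
- Number of relapse criteria needed: one.
- Progressive disease (PD), marrow component: an absolute percentage of at least 10%, that is [10, 100].

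**Overlap**
- CR and relapse from CR: [0, 5] ∩ [5, 100] = {5}. One value is shared.
- CR and PD: [0, 5] ∩ [10, 100] is empty. The fault is confined to the first pair.

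**Does another rule settle the shared value?**
- The two-consecutive-determinations rule in Section 6.3.2 covers serum M-protein, serum free light chains and urine M-protein. It does not cover the marrow percentage.
- The two-consecutive-measurements requirement in Section 6.3.3.1 belongs to PD. Relapse from CR carries no such requirement.
- Footnote o of the study calendar (Section 3.4) sets marrow timing and says when a repeat marrow may be omitted. It does not say how to classify a 5% reading.
- No rounding or tie-break rule for the marrow percentage appears in Sections 6.3.2 or 6.3.3 or in the calendar footnotes.

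**The clear case**
1. A patient enters CR with a marrow count below 5%.
2. A later marrow reads exactly 5%. Serum and urine immunofixation are still negative and there is no soft tissue plasmacytoma.
3. All CR conditions are still met, so the patient is in CR.
4. The count has risen to 5% since CR, so the relapse criterion is met.
5. If recurrent disease in Section 6.3.4 includes relapse from CR, which is its natural reading, duration of response both continues (step 3) and ends (step 4).

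The overlap carries into stringent CR, which inherits the 5% limit. The relapse line does not mention clonality, so a 5% marrow without clonal cells also meets both definitions.

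**After a change**
- CR < 5% with relapse ≥ 5%: [0, 5) ∩ [5, 100] is empty.
- CR ≤ 5% with relapse > 5%: [0, 5] ∩ (5, 100] is empty.

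Either change removes the conflict.

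**The case against.** The strongest reply is that the wording limits the problem. Relapse from CR can occur only in a patient already in CR, and the criterion speaks of development, which implies a change. This stands, and it rules out several stronger readings that a reader might infer.

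- **That a patient entering CR at 5% relapses on the same day, with a duration of zero.** The documents do not support this. Such a patient has not developed 5% after CR. The wording does not rescue the patient who was below 5% and rises to 5%, because that rise is a development.
- **That the CR rate is ambiguous.** It is not. As written, a 5% marrow with the other conditions met is CR. CR alone, VGPR+CR and ORR can be counted without difficulty.
- **That the number of affected patients can be estimated.** The documents give no distribution of marrow readings and no count of patients in CR. The interim figure in Section 1.2.10, 15/20, combines nCR with sCR, and nCR has no marrow criterion. The group that matters is also narrower than all CR marrows read as 5%: it is patients already in CR who later rise to exactly 5%.
- **That the boundary comes into play repeatedly.** This is not shown. Marrows are tied to milestones, and Section 5.1.1 makes them optional in the lenalidomide extension for patients who are MRD negative at the end of cycle 8. Footnote o waives some repeats, and footnote l makes the marrow at progression optional.

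It is also fair to say that only one descriptive secondary endpoint is plausibly touched. That bears on the size of the point; the two definitions still contradict each other.

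**Conclusion.** The point holds in a narrow form. The two definitions contradict each other for a patient already in CR at a lower count whose later marrow reads exactly 5% with the other CR conditions still met. For that patient, duration of response is not determined by the text. This rests on reading recurrent disease in Section 6.3.4 as including relapse from CR.

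The number affected is unknown and probably small. The grade 3 or worse neurologic toxicity endpoint, the stopping rule in the first 20 patients and the sample size of 45 do not use the marrow threshold. The effect on PFS is unclear: Section 6.3.5 counts progression or death, the PD marrow limit is 10%, and the plan does not say whether relapse from CR counts as progression. This is a minor correction, worth making because an endpoint rule should not give two answers to one reading.

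**What to change.** Reconcile the CR and relapse-from-CR entries in Section 6.3.3.1 by making one of the two inequalities strict, so that 5% falls in one category only. The documents do not show which should change. Section 6.3.3 attributes the response criteria to reference 31, so the sponsor should check both limits against that source and record the choice. Apply the chosen rule uniformly whenever response and duration of response are analysed, and fix it without regard to the later course of any patient with a 5% reading.

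The cost is one symbol and a check of marrow percentages already recorded. No new data are needed, and no sample size or error rate changes. The downside depends on the choice:
- If the CR limit is made strict, any patient counted as CR on a 5% marrow leaves that category and the CR rate may fall slightly. With 45 evaluable patients as the denominator, each such patient moves it by 1/45 = 2.2 percentage points.
- If the relapse limit is made strict, the CR rate does not change.
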